12.4.2 Statistical model, hypothesis, and method of analysis

To address the co-primary efficacy objectives:

Region-level CLR and its 95% CI will be calculated using logistic random-effects models taking into account the correlation among regions within one patient. .The lower bound of the 95% CI for CLR should be greater than 0.5 to attain the first co-primary endpoint.

Patient-level PPV and its 95% CI will be calculated based on the binomial distribution. The lower bound of the 95% CI for patient-level PPV should be greater than 0.2 to attain the second co-primary endpoint.

12.4.3 Handling of remaining intercurrent events of primary estimand

The primary analyses will account for intercurrent events as explained in the following:

Patients receive the investigational imaging agent [18F]CTT1057 but do not undergo/complete the PET/CT scan for any reasons: they will not be used for the co-primary endpoint analyses, but safety data will be collected as planned after the administration of the investigational imaging agent.

12.4.4 Handling of missing values not related to intercurrent event

This is a diagnostic study, co-primary endpoints are calculated on the basis of one-time imaging assessment, missing data not related to intercurrent events will not be imputed.

12.4.5 Sensitivity analyses for primary endpoint/estimand

The lower level of CTS will be used to verify positivity or negativity for the sensitivity analysis. For instance, if pathology (CTS Level 1) is used as true standard for primary estimand, imaging component of CTS (Level 2) will be used as true standard for sensitivity analysis for primary estimand. However, for those using changes in PSA level (CTS Level 3) as the true standard for primary estimand, their positivity status cannot be replaced by another component of CTS for sensitivity analysis.

Supplementary analysis 12.4.6

As supplementary analyses performed in the EFF, the region-level CLR and patient-level PPV and 95% CIs will be obtained from covariate adjusted logistic regression model. Important covariate will be specified in the SAP.

Subgroup analyses for region-level CLR and patient-level PPV will be performed:

patients with prior radical prostatectomy

patients with prior curative intent radiation therapy

If the co-primary endpoints are met, other subgroup analyses to assess the homogeneity of the treatment effect across demographic and baseline disease characteristics will be performed. Other subgroups will be specified in the SAP. Further supplementary analyses will be specified in the SAP.

12.5 Analysis of secondary endpoints/estimands

The secondary objectives and related endpoints are described in Table 2-1.

12.5.1 Efficacy and/or Pharmacodynamic endpoint(s)

Following secondary endpoints, centralized imaging assessment will be used as reference standard if pathology assessment is not available for a lesion.

Patient-level sensitivity is defined as the proportion of TP patients among those who are TP or

Patient-level specificity is defined as the proportion of TN patients among those who are TN or FP

Patient-level negative predictive value is defined as the proportion of TN patients among those who are TN or FN

Patient-level accuracy is defined as the proportion of TP and TN patients among all scanned patients (regardless of TP, TN, FP, FN)

Patient-level correct detection rate is defined as the proportion of TP patients among all scanned patients (regardless of TP, TN, FP, FN)

Patient-level detection rate is defined as the proportion of TP and FP patients among all scanned patients (regardless of TP, TN, FP, FN)

where TP, TN, FP, FN patients are defined as follows:

- PSMA TP patients are those who have at least one TP lesion with anatomically localized correspondence between [18F]CTT1057 PET imaging and the CTS.
- PSMA TN patients are those who do not show any pathological [18F]CTT1057 uptake and will be confirmed NOT having any lesions with the CTS.
- PSMA FP patients are those who show at least one pathological [18F]CTT1057 uptake but will be verified NOT having any lesions with the CTS or none is correctly localized in anatomical location by the CTS.
- PSMA FN patients are those who do not show any pathological [18F]CTT1057 uptake but will be confirmed having at least one with the CTS.

Number of TP, TN, FP, FN patients will be presented and used to calculate the diagnostic performance parameters.

95% CI for diagnostic performance parameters will be calculated based on the binomial distribution.

[18F]CTT1057 scan inter-reader variability is defined as agreement among three readers determinations and will be assessed by Fleiss' Kappa statistic. Details of calculation of Fleiss' Kappa statistic in SAP.

[18F]CTT1057 scan intra-reader variability is defined as within-reader agreement for two different time points and will be assessed by Cohen's Kappa statistic. A subset of imaging reading will be performed at two different time points by each reader. See details in imaging charter. Details of calculation of Cohen's Kappa statistic in SAP.

Change in patient management plans attributed to the [18F]CTT1057 PET/CT scan is defined as the percentage of patients who undergo a change in intended treatment plan attributed to the PET/CT scan as assessed by pre imaging questionnaire 1 and post imaging questionnaire 2

Numbers and percentage of patients on each category of treatment plan: surgery, radiation alone, radiation alone with change in radiation treatment plan (only applicable for questionnaire 2), radiation plus ADT, ADT alone, observation/surveillance, other (free text box) in two questionnaires will be calculated.

Treatment plan change is defined as a pair of categories (one category of questionnaire 1, one category of questionnaire 2)

Numbers and percentage of patients on the treatment change defined above will be calculated.

The following secondary endpoints, centralized imaging assessment will be used as reference standard if pathology assessment is not available for a lesion.

Region-level sensitivity is defined as the proportion of TP regions among those that are TP or FN

Region-level specificity is defined as the proportion of TN regions among those that are TN or

Region-level negative predictive value is defined as the proportion of TN regions among those that are TN or FN

Region-level accuracy is defined as the proportion of TP and TN regions among those that are identified on [18F]CTT1057 (regardless of TP, TN, FP, FN)

where TP, TN, FP, FN regions are defined as follows:

- PSMA TP regions are regions containing at least one TP lesion (anatomically localized correspondence between [18F]CTT1057 PET imaging and the CTS).
- PSMA TN regions are regions containing no lesions with pathological [18F]CTT1057 uptake and confirmed by CTS.
- PSMA FP regions are regions containing lesions with pathological [18F]CTT1057 uptake but will be verified negative by CTS or none is correctly localized in anatomical location by the CTS.
- PSMA FN regions are regions containing no lesions with pathological [18F]CTT1057 uptake but will be confirmed having at least one lesions with the CTS.

Number of TP, TN, FP, FN regions will be presented and used to calculate the diagnostic performance parameters.

95% CI for region-level diagnostic performance parameters will be calculated using logistic random-effects models taking into account the correlation among regions within one patient.

For different regions (i.e. prostate region, PLN, extra-PLN, skeletal, visceral), 95% CI for region-level diagnostic performance parameters will be calculated based on the binomial distribution respectively.

Patient-level positive predictive value will be also calculated for different categorical PSA levels.

Concordance between [18F]CTT1057 and [68Ga]Ga-PSMA-11 for detection of lesions, positive percent agreement will be calculated to assess the concordance.

12.5.2 Safety endpoints

Safety summaries (tables, figures) include only data from the on-treatment period with the exception of baseline data which will also be summarized where appropriate (e.g. change from baseline summaries). In addition, a separate summary for death including on treatment and post treatment deaths will be provided. In particular, summary tables for adverse events (AEs) will summarize only on-treatment events, with a start date during the on-treatment period (treatment-emergent AEs). [18F]CTT1057 treatment-emergent AEs, [68Ga]Ga-PSMA-11 treatment-emergent AEs will be presented using F-SAF and Ga-SAF separately.

The overall observation period will be divided into three mutually exclusive segments:

- 1. Pre-treatment period: from day of participant's informed consent to the day and time before dosing of study treatment
- 2. On-treatment period: from day of dosing of study medication to approximately 14 days after dosing of study treatment.
- 3. Post-treatment period: starting at day 15 after dosing of study medication.

Adverse events

All information obtained on adverse events will be displayed by participant.

The number (and percentage) of participants with treatment emergent adverse events (events started after the first dose of study medication or events present prior to start of study treatment but increased in severity based on preferred term) will be summarized in the following ways:

- primary system organ class and preferred term.
- primary system organ class, preferred term and maximum severity.
- Standardized MedDRA Query (SMQ) and preferred term.

Separate summaries will be provided for study medication related adverse events, death, serious adverse events, other significant adverse events leading to drug interruption, and adverse events leading to drug withdrawn.

A participant with multiple adverse events within a primary system organ class is only counted once towards the total of the primary system organ class.

Summary tables for adverse events (AEs) will include only AEs that started or worsened during the on-treatment period, the treatment-emergent AEs.

The incidence of treatment-emergent adverse events (new or worsening from baseline) will be summarized by system organ class and or preferred term, severity (based on CTCAE grades), type of adverse event, relation to study treatment.

Serious adverse events, non-serious adverse events during the on-treatment period will be tabulated.

All deaths (on-treatment and post-treatment) will be summarized.

All AEs, deaths, and serious adverse events (including those from the pre and post-treatment periods) will be listed and those collected during the pre-treatment and post-treatment period will be flagged.

Vital signs

All vital signs data will be listed by participant, and visit/time and clinically notable values or changes in vital signs will be flagged. Summary statistics will be provided by visit/time.

12-lead ECG

All ECG data will be listed by participant and visit/time, abnormalities will be flagged. Summary statistics will be provided by visit/time.

Clinical laboratory evaluations

All laboratory data will be listed by participant and visit/time and if normal ranges are available abnormalities will be flagged. Summary statistics will be provided by visit/time. Shift tables using the low/normal/high/ (low and high) classification will be used to compare baseline to the worst on-treatment value.

Grading of laboratory values will be assigned programmatically as per National Cancer Institute (NCI) CTCAE version 5.0. The calculation of CTCAE grades will be based on the observed laboratory values only, clinical assessments will not be taken into account.

CTCAE Grade 0 will be assigned for all non-missing values not graded as 1 or higher. Grade 5 will not be used.

For laboratory tests where grades are not defined by CTCAE version 5.0, results will be categorized as low/normal/high based on laboratory normal ranges.

The following listings/summaries will be generated separately for hematology, and biochemistry tests:

Listing of all laboratory data with values flagged to show the corresponding CTCAE version 5.0 grades if applicable and the classifications relative to the laboratory normal ranges

[figure not shown]
For laboratory tests where grades are defined by CTCAE version 5.0:

- Worst post-baseline CTCAE grade (regardless of the baseline status). Each participant will be counted only once for the worst grade observed post-baseline.
- Shift tables using CTCAE version 5.0 grades to compare baseline to the worst ontreatment value

For laboratory tests where grades are not defined by CTCAE version 5.0:

Shift tables using the low/normal/high/ (low and high) classification to compare baseline to the worst on-treatment value.

In addition to the above mentioned tables and listings, other , for example, figures plotting time course of raw or change in laboratory tests over time or box plots might be specified in the analysis plan.

12.7 **Interim analyses**

Not applicable

12.8 Sample size calculation

Overall, approximately 190 participants will be enrolled to ensure at least 152 participants are evaluable (i.e. have both an evaluable [18F]CTT1057 PET/CT scan imaging, and at least one evaluable CTS assessment and have not received any prohibited systemic antineoplastic therapy before the completion of PET/CTs and CTS procedures), which will be required for the calculation of the co-primary endpoints. These calculations were made using the software PASS 11 and R 3.6.1.

Primary endpoint(s) 12.8.1

This study is planned to recruit approximately 190 patients. The sample size calculation is based on the co-primary endpoints of region-level CLR and the patient-level PPV of [18F]CTT1057.

The assumptions for sample size calculations are based on the estimates from data available from prior studies.

The primary endpoint is to evaluate region-level CLR (prostate region, PLN, extra-PLN, skeletal, visceral) and patient-level PPV of [18F]CTT1057 PET for detection of tumor location confirmed by histopathology/biopsy. Based on the results of previous studies, the following distribution of disease across regions are anticipated: Prostate bed: 30%, pelvis: 15%; extrapelvic soft tissue: 20%; bone metastases: 35% (Eiber et al 2015, Ceci et al 2015, Van Leeuwen et al 2016). It is anticipated that the CLR for the five regions and for all regions combined using conventional imaging ranges from 30-60%. An overall CLR for [18F]CTT1057 PET of at most 50% will be considered as unacceptably low. Hence, the null hypothesis that the CLR is at most 50% will be tested against the alternative hypothesis that the CLR is greater than 50%.

The BCR population targeted in this study is expected to have similar PSA values than prior studies (Morris et al 2020) of approved diagnostic PET agents for PCa such as [18F]fluciclovine, which had a 27% PPV for patients with PSA values that were less than 1.78, as noted in their summary basis of approval. Thus, a patient-level PPV of 20% will be considered as unacceptably low. The [18F]CTT1057 positive patient rate (detection rate) for the study population is 80% based on [18F]-fluciclovine studies. The sample size calculation will be performed based on the null and alternative hypotheses as follows.

Region-level CLR:

Correlated binary test results occur in this situation where each experimental unit (patient) consists of five correlated regions. Lee and Dubin developed a sample size formula for clustered binary data (Lee and Dubin 1994). They propose estimating the binary proportion by assigning equal weights to clusters regardless of their sizes to simplify the derivation of their sample size formula. The weighted estimator for region-level CLR is approximately Gaussian distributed with a variance of a beta distribution (beta-binomial model).

The null Hypothesis H0: region-level CLR p = 0.5 will be tested against the alternative hypothesis H1: p > 0.5 Assuming a CLR of 0.58 under the alternative hypothesis, a total sample size of 172 enrolled participants would achieve 90% statistical power to detect a change in CLR of 0.08 using a one-sided test at a target significance level of 2.5%. This sample size includes an adjustment for a dropout rate of 0.20.

To determine the sample size n such that the type I error of one-sided testing H0 is 0.025 and with power 0.9 to reject H0 if alternative H1 is true. By the standard normal approximation, the sample size is given

Amended Protocol (Version No. 01 Clean)

$$n = \frac{\sigma^2 (Z_{\alpha} - Z_{1-\beta})^2}{(p_1 - p_0)^2}$$

where σ^2 the variance of a beta distribution, Z_a is the upper a quantile of the standard normal distribution, p_0 is the CLR 0.5 under null hypothesis, p_1 is 0.58 the achievable CLR.

Suppose there is no information on the within-cluster correlation of test results. In this case, a uniform distribution seems reasonable, setting parameters in the beta distribution alpha=1 and beta=1. Then σ^2 is 1/12

Under these assumptions, 137 patients will be necessary to ensure the 90% power, taking into account 20% dropout rate, a total of 172 patients will be recruited for this endpoint of the study.

The lower bound of the 95% CI for CRL should be greater than 0.5 to be considered success.

• Patient-level PPV

The null Hypothesis H0: patient-level PPV p = 0.2 will be tested against the alternative hypothesis H1: p > 0.2 Assuming a patient-level PPV of 0.33 under the alternative hypothesis, a total sample size of 190 enrolled participants (which includes 152 [18 F]CTT1057 scanned patients based on 80% [18 F]CTT1057 positive patient rate) would achieve 90% statistical power to detect a change in patient-level PPV of 0.13 using a one-sided binomial test at a target significance level of 2.5%. This sample size includes an adjustment for a dropout rate of 20%. The lower bound of the 95% CI for patient-level PPV should be greater than 0.2 to be considered success.

A total sample size of 190 patients can ensure 92.7% statistical power for region-level CLR and 90% statistical power for patient-level PPV resulting in an overall study statistical power of at least 83.4% (0.927*0.9).

13 Ethical considerations and administrative procedures

13.1 Regulatory and ethical compliance

This clinical study was designed and shall be implemented, executed and reported in accordance with the ICH Harmonized Tripartite Guidelines for GCP, with applicable local regulations (including European Directive 2001/20/EC, US CFR 21), and with the ethical principles laid down in the Declaration of Helsinki.

13.2 Responsibilities of the investigator and IRB/IEC

Before initiating a trial, the investigator/institution must obtain approval/favorable opinion from the Institutional Review Board/Independent Ethics Committee (IRB/IEC) for the trial protocol, written informed consent form, consent form updates, participant recruitment procedures (e.g., advertisements) and any other written information to be provided to participants. Prior to study start, the investigator is required to sign a protocol signature page confirming his/her agreement to conduct the study in accordance with these documents and all of the instructions and procedures found in this protocol and to give access to all relevant data and records to Novartis monitors, auditors, Novartis Quality Assurance representatives, designated agents of Novartis,

IRBs/IECs, and regulatory authorities as required. If an inspection of the clinical site is requested by a regulatory authority, the investigator must inform Novartis immediately that this request has been made.

13.3 Publication of study protocol and results

The protocol will be registered in a publicly accessible database such as clinicaltrials.gov and as required in EudraCT. In addition, after study completion and finalization of the study report the results of this trial will be submitted for publication and posted in a publicly accessible database of clinical trial results, such as the Novartis clinical trial results website and all required Health Authority websites (e.g. Clinicaltrials.gov, EudraCT etc.).

For details on the Novartis publication policy including authorship criteria, please refer to the Novartis publication policy training materials that were provided to you at the trial investigator meetings.

13.4 **Quality Control and Quality Assurance**

Novartis maintains a robust Quality Management System (QMS) that includes all activities involved in quality assurance and quality control, to ensure compliance with written Standard Operating Procedures as well as applicable global/local GCP regulations and ICH Guidelines.

Audits of investigator sites, vendors, and Novartis systems are performed by auditors, independent from those involved in conducting, monitoring or performing quality control of the clinical trial. The clinical audit process uses a knowledge/risk based approach.

Audits are conducted to assess GCP compliance with global and local regulatory requirements, protocols and internal Standard Operating Procedures (SOPs), and are performed according to written Novartis processes.

14 Protocol adherence

This protocol defines the study objectives, the study procedures and the data to be collected on study participants. Additional assessments required to ensure safety of participants should be administered as deemed necessary on a case by case basis. Under no circumstances including incidental collection is an investigator allowed to collect additional data or conduct any additional procedures for any purpose involving any investigational drugs under the protocol, other than the purpose of the study. If despite this interdiction prohibition, data, information, observation would be incidentally collected, the investigator shall immediately disclose it to Novartis and not use it for any purpose other than the study, except for the appropriate monitoring on study participants.

Investigators ascertain they will apply due diligence to avoid protocol deviations. If an investigator feels a protocol deviation would improve the conduct of the study this must be considered a protocol amendment, and unless such an amendment is agreed upon by Novartis and approved by the IRB/IEC and Health Authorities, where required, it cannot be implemented.

16.1 Appendix 1: Common Terminology Criteria for Adverse Events

The complete NCI CTCAE (version 5.0) can be found at the following site:

 $[ctep.cancer.gov/protocolDevelopment/electronic_applications/docs/CTCAE_v5_Quick_Reference_8.5x11.pdf]$

The latest RECIST guidelines (version 1.1) can be found at the following site: [project.eortc.org/recist/wp-content/uploads/sites/4/2015/03/RECISTGuidelines.pdf]

16.3 Appendix 3: PCWG3

The sections that apply to this trial are the criteria for PSA response and progression, and the criteria for bone lesion "prevent/delay end points" (progression). It is based on the PCWG3 recommendations (Scher et al 2016).

16.4 Appendix 4: Patient Management questionnaire

A questionnaire on the planned patient management will be filled-in by the treating physician/Clinical Study Investigator before (questionnaire 1) and within 14 days after knowing the results of the [18F]CTT1057 PET/CT scan (questionnaire 2).

Options will be given in the questionnaire to capture possible management plan, such as

- Surgery
- Radiation alone
- Radiation alone with change in radiation treatment plan (only applicable for questionnaire 2)
- Radiation plus ADT
- ADT alone
- Observation/surveillance
- Other (free text box)

The results of the [¹⁸F]CTT1057 PET/CT scan will be provided to the Study Investigator before the patient undergoes the planned treatment by a local nuclear medicine physician or radiologist with expertise in reading oncology PET/CT scans, who will be blinded to [⁶⁸Ga]Ga-PSMA-11 data but not to other patient data, in order to reproduce as much as possible the real clinical context to assess the potential clinical impact of the investigational procedure.

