Section 3	Clarification on Standard of Care	Clarification that the high resolution CT
Section 4.1	imaging part of CTS	scan and any other imaging diagnostic procedure clinically indicated as per SoC
Section 8.3.1	level 2 timing	part of CTS level 2 must be acquired
	10 / 01 = vg	within the 8 weeks either prior to or
		following the [18F]CTT1057 PET/CT scan.
Section 8.3.1	Addition of Table 8-2	Addition to provide clarity to sites on the
		imaging procedures expected for this study
		and their timing. Subsequent tables in the
		document were re-numbered accordingly.
Section 8.3.1		
Section 8.3.1	Clarification on	Clarification that the characteristics of
Section 6.3.1	Characteristics of	lesions should be documented for lesions
	lesions	that are visually positive on the [68Ga]Ga-
		PSMA-11 PET but not considered as
		prostate cancer (i.e. non prostate cancer
		tumoral lesions, or benign non tumoral
		lesions).
Section 3	Addition of a new	Addition of a new option named
Section 12.5.1	option in questionnaire	"Radiation alone with change in radiation
Section 16.4	#2	treatment plan", which will be applicable
(Appendix 4)		only for questionnaire 2, in order to capture any intended change in the radiation plan
		any michaed change in the fadiation plan

		(e.g. change in the extent of the field of radiations).
Section 6.2.1	Clarification of use of diuretics	Clarification that the use of diuretics (e.g. furosemide) to help subject to void before PET/CT scan imaging acquisition is allowed in case of need, upon the discretion of the investigator.
Section 6.2.2	Clarification of use of LHRH analogues and anti- androgens	Clarification that use of any ADT including LHRH analogues (agonists or antagonists) as well as anti-androgens (both first and second generation compounds) and 5-alpha reductase inhibitors is prohibited prior to completing both PET imaging scans and CTS procedures, to ensure that the same lesions are assessed on PET/CT scans and CTS procedures without potential reduction in lesion size and therefore detectability due to administration of antineoplastic medications.
Section 8.5.1	Clarification of patient management questionnaire #2 Timing for completion	Clarification that patient management questionnaire 2 should be completed before [⁶⁸ Ga]Ga-PSMA-11 PET/CT is performed for subjects assigned to sequence 1.

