Evaluate detection rate	 Proportion of patients who have at least one PET positive lesion, regardless of TP or FP findings, out of all patients who are scanned 		
Evaluate the region level sensitivity of [18F]CTT1057	 Proportion of regions that test positive on both [18F]CTT1057 and CTS (TP) among those regions that are CTS positive (TP or FN) 		
Evaluate the region level specificity of [18F]CTT1057	Proportion of regions that test negative on both [18F]CTT1057 and CTS (TN) among those regions that are CTS negative (FP, or TN)		
Evaluate the region level negative predictive value of [¹⁸ F]CTT1057	Proportion of regions that are CTS and [18F]CTT1057 negative (TN) among those regions that test negative on [18F]CTT1057 (TN or FN)		
Evaluate the region level accuracy of [18F]CTT1057	 Proportion of regions that are CTS and [¹8F]CTT1057 positive (TP) and negative (TN) among those regions that identified on [¹8F]CTT1057 (TP, TN, FP and FN) 		
Evaluate the patient-level positive predictive value related to PSA levels	Percentage of patients who have at least one TP lesion (exactly anatomically localized correspondence between [¹8F]CTT1057 PET imaging and the reference standard), regardless of any co-existent FP findings, out of all patients who are [¹8F]CTT1057 positive, stratified by PSA levels		
Characterize the safety and tolerability of [18F]CTT1057	Incidence of AEs Treatment emergent adverse event (TEAE) rate within 14 days after each PET tracer administration		

Amended Protocol (Version No.	01 Clean)
Allieliaea i Totocoi (VEISION INC	. U i Cicaii)

Objective(s)	Endpoint(s)	
• [¹⁸ F]CTT1057 scan inter-reader variability	Inter-reader agreement of [18F]CTT1057 images	
• [¹⁸ F]CTT1057 scan intra-reader variability	Intra-reader agreement of [18F]CTT1057 images	
 Concordance between [¹⁸F]CTT1057 and [⁶⁸Ga]Ga-PSMA-11 for detection of lesions at lesion level using central reads 	Concordance between [18F]CTT1057 and [68Ga]Ga-PSMA-11 for detection of PSMA-positive lesions (location and number) using central reads	
 Evaluate the change in patient management plans attributed to the PET/CT scan 	Percentage of patients who underwent a change in intended treatment plan attributed to the PET/CT scan as assessed by pre and post imaging questionnaires	

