Change in patient management plans attributed to the [18F]CTT1057 PET/CT scan is defined as the percentage of participants who undergo a change in intended treatment plan attributed to

the PET/CT scan as assessed by pre-imaging questionnaire 1 and post-imaging questionnaire 2.

The number and percentage of participants from the F-SAF for each of the following categories of treatment plan in each of the two questionnaires will be calculated: surgery, radiation alone, radiation alone with change in radiation treatment plan (only applicable for questionnaire 2), radiation plus ADT, ADT alone, observation/surveillance, other (free text box).

Treatment plan change is defined as a change in the pair of categories (one category of questionnaire 1, one category of questionnaire 2).

The number and percentage of participants from the F-SAF with treatment plan change as defined above will be calculated. Shift tables comparing treatment plans between questionnaire 1 and 2 will be displayed. The number (%) of participants with and without a change in treatment plans by [18F]CTT1057 local read results (i.e. positive, negative, and inconclusive) will be tabulated.

**Region-level sensitivity** is defined as the proportion of TP regions among those that are TP or FN

**Region-level specificity** is defined as the proportion of TN regions among those that are TN or FP

**Region-level negative predictive value** is defined as the proportion of TN regions among those that are TN or FN

**Region-level accuracy** is defined as the proportion of TP and TN regions among those that are identified on [18F]CTT1057 (regardless of TP, TN, FP, FN)

where TP, TN, FP, FN regions are defined as follows:

- PSMA TP regions are regions containing at least one TP lesion (anatomically localized correspondence between [18F]CTT1057 PET imaging and the CTS).
- PSMA TN regions are regions containing no lesions with pathological [18F]CTT1057 uptake and confirmed by CTS.
- PSMA FP regions are regions containing lesions with pathological [F]CTT1057 uptake but are verified negative by CTS or none is correctly localized in anatomical location by the CTS.
- PSMA FN regions are regions containing no lesions with pathological [F]CTT1057 uptake but are confirmed as having at least one lesion with the CTS.

Number of TP, TN, FP, FN regions will be presented and used to calculate the diagnostic performance parameters.

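### Questionnaire 2 offers a structured changed-radiation-plan option only under radiation alone, so the same change within radiation plus ADT is normally scored as no change

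*Protocol*

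**What the plan says.** Protocol Table 2-1 defines the endpoint as "Percentage of patients who underwent a change in intended treatment plan attributed to the PET/CT scan as assessed by pre and post imaging questionnaires". Nothing restricts it to particular treatment pathways.

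The response options are the same in Protocol Sections 3, 12.5.1 and 16.4 and in SAP Sections 1.1 and 2.6.1. Radiation alone has a second version for the post-scan form only: "Radiation alone with change in radiation treatment plan (only applicable for questionnaire 2". The combined option is the single entry "Radiation plus ADT", with no changed-plan version. The list ends with "Other (free text box".

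SAP Section 2.6.1 gives the scoring rule: "Treatment plan change is defined as a change in the pair of categories (one category of questionnaire 1, one category of questionnaire 2". Protocol Section 12.5.1 rests on the same basis: "Treatment plan change is defined as a pair of categories (one category of questionnaire 1, one category of questionnaire 2". The SAP also plans shift tables between the two questionnaires, and a tabulation of change by local read result.

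The summary of changes for Protocol Amendment 01 explains that the radiation-alone option was added "in order to capture any intended change in the radiation plan", and its example is a "change in the extent of the field of" radiation.

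**The concern.** The stated aim of the added option is to capture any intended change in the radiation plan, but the option covers only one of the two radiation pathways on the form. A scan that leads the physician to alter the radiation plan counts towards the endpoint if the participant is to have radiation alone. It does not count if ADT is given as well.

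The reported percentage therefore depends partly on how many participants fall into the combined category, and not only on how often the scan altered the plan. The secondary objectives are also to be assessed separately after prior prostatectomy and after prior curative-intent radiation. If use of radiation plus ADT differs between those subgroups, the undercount differs too, and the contrast between them is distorted.

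**Working it through.** The documents give no expected rate, threshold or power for this endpoint, so there is no figure to reproduce. The check applies the scoring rule to the option lists.

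**Step 1: options.** Questionnaire 1 has six: surgery, radiation alone, radiation plus ADT, ADT alone, observation/surveillance, other. Questionnaire 2 has these six plus radiation alone with a changed radiation plan, so seven.

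**Step 2: apply the rule.** There are 6 × 7 = 42 possible pairs. Six are identical and score as no change. The other 36 score as change.

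**Step 3: place the same event in each pathway.**

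| Plan before the scan | Event after the scan | Pair recorded | Score |
|---|---|---|---|
| Radiation alone | Radiation plan altered | Radiation alone → radiation alone, changed plan | Change |
| Radiation plus ADT | Radiation plan altered, ADT kept | Radiation plus ADT → radiation plus ADT | No change |
| Radiation plus ADT | Same, but entered as free text | Radiation plus ADT → other | Change |

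The third row depends on the individual physician. No passage directs sites to use free text here, and radiation plus ADT still describes the plan correctly.

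**Step 4: direction and size.** Let x be the reported change rate, c the share of participants with radiation plus ADT on both forms, and f the fraction of those whose radiation plan was altered because of the scan.

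- Undercount from this cell = c × f, which cannot be negative.
- Rate corrected for this cell = x + c × f, which lies between x (f = 0) and x + c (f = 1).

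Both c and f are assumptions. For illustration only:

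- c = 10%, f = 10%: 0.10 × 0.10 = 1 percentage point.
- c = 20%, f = 30%: 0.20 × 0.30 = 6 points.
- c = 40%, f = 50%: 0.40 × 0.50 = 20 points.

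If all 190 planned participants were in the [18F]CTT1057 safety set, on which the endpoint is analysed, the two extremes would be 190 × 0.01 = 1.9 and 190 × 0.20 = 38 participants. So wide a range shows that the documents do not determine the size.

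**Step 5: which bounds are valid.** One could report the rate with the cell counted as unchanged, and again with the cell removed as not assessable. That interval need not contain the corrected value. Take x = 20%, c = 30%, f = 40%:

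- Corrected value: 20% + 0.30 × 0.40 = 32%.
- Cell removed from the denominator: 0.20 / 0.70 = 28.6%, so the interval is 20% to 28.6% and misses 32%.
- Whole cell counted as changed: 20% + 30% = 50%, so the interval is 20% to 50% and contains 32%.

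**The case against.** The strongest points on the other side are these.

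- **Free text is available, and the protocol introduces the list as examples.** This stands in part. A changed radiation plan within radiation plus ADT can be recorded, so a reader who infers that it cannot be captured at all goes too far. But the SAP tabulates exactly these categories, and neither document says when to use free text or how to classify it. Whether such a change counts is left to individual habit.
- **The shift table already shows the cell.** It shows the count. Nothing tells the reader that an altered radiation plan inside the cell was not captured, and the headline percentage treats everyone in it as unchanged.
- **The endpoint as a whole need not be too low.** This stands. Protocol Section 3 says a plan change should not rest on the [18F]CTT1057 scan alone, and the local reader sees other patient data. Changes prompted by other information between the two forms also score as change and push the rate up. The documents support a direction for this cell, not a net bias of the endpoint.
- **Other options are equally coarse.** Surgery to surgery with a different extent also scores as unchanged. This is fair: how finely to split categories is partly a matter of design, and closing this gap does not make all pathways comparable. Radiation differs because the sponsor chose to split it, for a reason that applies equally with ADT.
- **It is late.** Amendment 01 was made with 20 participants randomized and 12 dosed. The current SAP is dated 20 December 2023, after the dry run of the study report and before database lock. A new form option may reach few or no participants. The SAP changes need no new data.

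**Conclusion.** The point holds in limited form. Under the category-pair rule, a scan-driven change of radiation plan in a participant with radiation plus ADT on both forms is scored as no change, unless the physician chose free text. The same event within radiation alone is counted. This falls short of the amendment's stated purpose.

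The direction for this cell follows from the rule alone: it can only lower the percentage. The size is c × f and is not derivable, because no passage gives the expected frequency of any management option or of altered radiation plans. A reader might infer that radiation plus ADT is a common pathway here, or quote a specific number of missed percentage points. The documents support neither.

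The consequence is minor. The endpoint is secondary and descriptive, with no hypothesis or success threshold. The co-primary endpoints and the sample size are untouched.

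**What to change.** **Forms still to be completed.** Add to questionnaire 2 a radiation-plus-ADT counterpart of the changed-plan option, and count its selection as a change. This is one response option in the eCRF, carried into the matching lists in the protocol and SAP.

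**Forms already completed.** Add to SAP Section 2.6.1, before database lock, that:

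1. the cell for radiation plus ADT on both questionnaires is labelled in the planned shift table as not capturing changes to the radiation plan;
2. the change rate is reported with two bounds, counting that whole cell first as unchanged and then as changed;
3. free-text entries on questionnaire 2 that describe radiation plus ADT with an altered radiation plan are classified as a change.

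The SAP text needs no new data and little programming. The drawback is that earlier forms lack the detail, so for those participants the rate stays a range, which may be wide if the cell is large. The change concerns data capture and scoring only.
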